## 5.2 *Concomitant medication date imputation*

Partial concomitant medication start dates are imputed with reference to the treatment start date as outlined below.

Completely missing start dates will not be imputed.

Any missing date will be queried for resolution. For any unsolved missing dates, the following rules in the following order will be applied to decide if a concomitant medication or a significant non-drug therapy was taken after the start of the study treatment and to decide if the data should be included in the summary table. Originally collected date will be listed in listings.

CM start date imputation:

1. If the CM start date year value is missing, the imputed CM start date is set to one day prior to treatment start date.
2. If the CM start date year value is less than the treatment start date year value, the CM started before treatment. Therefore:
  - a. If the CM month is missing, the imputed CM start date is set to the mid-year point (01JulYYYY).
  - b. Else if the CM month is not missing, the imputed CM start date is set to the mid-month point (15MONYYYY).
3. If the CM start date year value is greater than the treatment start date year value, the CM started after treatment. Therefore:
  - a. If the CM month is missing, the imputed CM start date is set to the year start point (01JanYYYY).
  - b. Else if the CM month is not missing, the imputed CM start date is set to the month start point (01MONYYYY).
4. If the CM start date year value is equal to the treatment start date year value:
  - a. And the CM month is missing or the CM month is equal to the treatment start date month, then the imputed CM start date is set to one day prior treatment start date.
  - b. Else if the CM month is less than the treatment start date month, the imputed CM start date is set to the mid-month point (15MONYYYY).
  - c. Else if the CM month is greater than the treatment start date month, the imputed CM start date is set to the month start point (01MONYYYY).

CM end date imputation:

1. If CM end day is missing and CM month/year are non-missing then impute CM day as the minimum of treatment end date and the last day of the month.
2. If CM end day/month are missing and CM year is non-missing then impute CM day as the minimum of treatment end date and the end of the year (31DECYYYY).
3. If CM day/month/year is missing then use the treatment end date + 1 day as the imputed CM end date.
4. If imputed CM end date is less than the CM start date, use the CM start date as the imputed CM end date.

---

- If complete (imputed) CM end date is available and the imputed CM start date is greater than the (imputed) CM end date, then imputed CM start date should be set to the (imputed) CM end date.

## 6 VARIABLES AND ENDPOINTS

### 6.1 DERIVATION RULES

#### 6.1.1 AEs coding/grading

AEs will be graded according to the Common Terminology Criteria for Adverse Events (CTCAE) version 3.0.

If CTCAE grading does not exist for an AE, grades 1 to 4 corresponding to the severity of mild, moderate, severe, and life-threatening will be used. The CTC/severity grade will not be imputed if missing. CTC grade 5 (death) will not be used because the outcome of an AE is not recorded on the AE CRF pages.

#### 6.1.2 Study drug start and end date

Treatment start date for cohort 1: defined as the first date at which a non-zero dose of pasireotide s.c. was administered during the study and recorded on the DAR (e)CRF.

Treatment start date for cohort 2: defined as the first date at which a non-zero dose of pasireotide s.c. was administered prior to study entry and recorded on the CMD (e)CRF.

Treatment end date (same for the 2 cohorts) (The date of last administration of study drug) is defined as the last date at which a non-zero dose of study drug was administered and recorded on the DAR (e)CRF. If the end of the last dosing period with a non-zero dose is missing, the "last known date patient took study drug" (as reported on the completion panel (CMP)) will be used.

Date of first dose after informed consent (IFC): defined as the first date at which a non-zero dose of pasireotide s.c. was administered during the study (i.e. after IFC) and recorded on the DAR (e)CRF.

If treatment with pasireotide s.c. is still ongoing at the time of data cut-off for analysis (i.e. no end date on DAR and CMP (e)CRF), it will be assumed that treatment was ongoing until the last contact date (see Section 6.1.4).

Periods with a specific dose of study medication may have incomplete start and/or end dates (e.g. FEB2015 to MAR2015), however, it is assumed that month and year are always known. If the day is missing in the start date,

- the 15th of the respective month is used for imputation, if not before the end date of the previous period,
- the day after the previous end date is used otherwise.

After imputation of start dates, incomplete end dates are imputed. The unknown end date is set

- to one day before the next start date if the known month and year are equal to month and year of the next start - 1 day
- to the last day of the known month otherwise.

---

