### 6.1.4 Last contact date

The last contact date is defined as the latest date among the following:

- All assessment dates (e.g. vital signs assessment dates, dates at which questionnaires were completed, imaging dates, dates at which blood samples were taken, ECG dates, etc.)
- Medication dates including study medication and concomitant medications
- AEs start and end dates
- Last known date patient took study drug as reported on the completion panel

If any of the dates for the above measurements are partial dates, the earliest possible date will be used to impute the date (i.e. first day of month if month and year are known, first day of year if only the year is known).

If the last contact date is after the date of death, the last contact date will be set to the date of death.

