### 6.1.6 Baseline definition

The last non-missing assessment before or on the day of the patient's first dose during the study is considered the baseline assessment.

If no assessment is available before or on the day of first dose, the missing assessment may be imputed by the earliest post-dose assessment, provided it was performed within a pre-defined time window after first dose and before end of treatment.

Time windows depend on the type of assessment; they are displayed in Table 6-1. Baseline values assessed after first dose will not be used as post-baseline assessments.

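### SAP 6.1.2 imputes partial dose-period dates without checking the period's own other date, consent or death, so it can return impossible dates

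*SAP*

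**What the plan says.** SAP 6.1.2 provides for dose periods with an unknown day: "Periods with a specific dose of study medication may have incomplete start and/or end dates (e.g. FEB2015 to MAR2015". Month and year are assumed known. The rules are:

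- **Start:** "the 15th of the respective month is used for imputation, if not before the end date of the previous period"; failing that, "the day after the previous end date is used otherwise".
- **Order:** "After imputation of start dates, incomplete end dates are imputed".
- **End:** "to one day before the next start date if the known month and year are equal to month and year of the next start - 1" (the 1 is in days); failing that, "to the last day of the known month otherwise".

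The same section defines the first on-study dose as one given after consent, and SAP 4.1.1 defines Cohort 1 in the same sense. The treatment end is the last non-zero dose on the dose record. The completion-panel last-dose date is used when the end of the last period is *missing*. The section does not say whether a month-year end is *missing* in that sense or merely *incomplete*.

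Other dates in the SAP do have bounds. Section 5.1 limits imputed AE end dates by death and repairs a start that falls after the end. Section 5.2 repairs the order of concomitant-medication dates. Section 6.1.4 says: "If the last contact date is after the date of death, the last contact date will be set to the date of death".

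**The concern.** A start is compared only with the period before it, and an end only with the period after it. Neither is compared with the other date of its own period. There is no floor at consent for the first on-study period and no cap at death for the last. What is at stake depends on which period is affected:

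- **Interior period:** a negative or zero length distorts cumulative dose, mean daily dose and the counts of dose changes.
- **First on-study period:** the start is Day 1, which fixes study day, the time windows and baseline ("The last non-missing assessment before or on the day of the patient's first dose during the study is considered the baseline assessment"). If Day 1 is too early, a true pre-dose value becomes post-baseline. Table 6-1, which allows a post-dose baseline, is headed as applying to Cohort 2 only, so a new user may be left without a baseline.
- **Last period:** the end is the day of last dose. It sets duration of exposure, the on-treatment limit (3 days after last dose for efficacy, 28 for safety) and the 90-day window.

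**Working it through.** The plan gives no figure to reproduce, so I applied the 6.1.2 rules literally to hypothetical records. Length = end - start + 1, the form used for duration in SAP 8.3. The SAP's own example, FEB2015 to MAR2015, becomes 15 Feb to 31 Mar: 14 + 31 = 45 days, with no conflict.

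**1. Interior periods**

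| Record | Imputed | Length |
|---|---|---|
| Start FEB2015, known end 10 Feb | 15 Feb to 10 Feb | 10 - 15 + 1 = -4 |
| Start FEB2015, known end 14 Feb | 15 Feb to 14 Feb | 0 |
| FEB2015 to FEB2015, next start FEB2015 | both starts 15 Feb, so first end 14 Feb | 0 |
| Known start 20 Feb, end FEB2015, next start FEB2015 | 20 Feb to 14 Feb | 14 - 20 + 1 = -5 |

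In the first pattern, any known end from 1 to 14 February gives a length from -13 to 0. The third and fourth arise because starts are imputed before ends, so a partial previous end is not yet available to the start rule.

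**2. First on-study period**

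There is no previous period, so FEB2015 becomes 15 Feb. Any consent on 16 to 28 February is then later than Day 1. Take consent on 20 Feb, a true first dose on 24 Feb and a laboratory sample on 20 Feb:

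- True study day of the sample: 20 - 24 = -4, so it is eligible as baseline.
- Imputed study day: 20 - 15 + 1 = 6, inside the Month 1 window (days 2 to 60 in Table 6-2).

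Size per affected record, assuming true days uniform over a 365-day year and dosing on the day of consent: days after the 15th number 7×16 + 4×15 + 13 = 185, and 185/365 = 51%. The mean gap is (7×136 + 4×120 + 91)/185 = 8.2 days, with a maximum of 16.

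**3. Last period, if a month-year end is treated as incomplete**

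An end of MAR2015 becomes 31 Mar.

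- *Death on 10 Mar:* the last dose is 21 days after death. Exposure from 1 Jan is 90 days instead of 69. The rate denominator in SAP 6.2.4 takes the earliest of last dose + 28 days, last contact and cut-off. With last contact limited to 10 Mar it is 69 days either way.
- *Exact completion-panel date of 12 Mar:* the last dose is 19 days late. The efficacy limit (+3) moves from 15 Mar to 3 Apr, the safety limit (+28) from 9 Apr to 28 Apr, and day 90 from 10 Jun to 29 Jun.

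The largest overshoot is 31 - 1 = 30 days. With true days uniform over the year, the mean is (7×465 + 4×435 + 378)/365 = 14.7 days. It exceeds the 3-day efficacy gap on 7×27 + 4×26 + 24 = 317 of 365 days (87%).

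**The case against.** Much of the case on the other side stands and narrows the point.

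- **The rule does look forward.** It is tempting to say that it checks only the previous period. That is true of starts; the end rule uses the next start.
- **Interior errors stay local.** Duration of exposure in SAP 8.3 runs from treatment start to treatment end, so a bad interior period does not move Day 1, last dose, baseline or windows.
- **Rates are not carried past death.** A reader might infer inflated person-time. SAP 6.2.4, with 6.1.4 and the cut-off rule in 4.1, prevents person-time beyond death, last contact or cut-off. The cap does not correct a wrong Day 1, and a late last dose can still lengthen person-time up to last contact in a living patient.
- **The last-dose limb depends on a reading.** If a month-year end counts as *missing*, an exact completion-panel date is used and most of that limb disappears.
- **Consent is in the definition.** The first on-study dose is defined as after consent. That shows the imputation rule conflicts with its own definition; it does not repair the rule.
- **The record may be rare.** New users start at the first visit (Protocol 3.3.1.1; deviation I06), Table 3-1 suggests a dose record at baseline, and missing values are queried (Protocol 5.3).
- **Late imputation is not this defect.** On the same uniform assumption, 168/365 = 46% of partial starts are imputed too late. That is the ordinary error of any mid-month convention.
- **Part of the specification is out of sight.** SAP 8.3 refers to CSR Appendix 16.1.9 for these dates. It may add bounds, but the SAP text does not state them.

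**Conclusion.** The rule in 6.1.2 is wrong as written. It is stated for records that the SAP expects, and followed literally it returns periods of zero or negative length and a first on-study dose before consent. It can also return a last dose after death or after an exact completion-panel date, provided that a month-year end is read as incomplete. Comparable repairs already exist for AE and concomitant-medication dates.

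The size is known only per affected record: lengths down to -13 days in the February example, Day 1 up to 16 days before consent, and last dose up to 30 days late. The 51%, 14.7-day and 87% figures rest on uniform dates; the 51% also assumes dosing on the consent day. The month-end overshoot is a demonstrable error only where death or an exact last-dose date contradicts it. The documents do not say how many dose dates are partial, so no total effect follows.

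A reader might infer that the primary endpoint, the percentage of patients with related AEs and SAEs, is biased. The documents give nothing from which to show or size such a change, and the study is descriptive with no hypothesis tests. The correction should be made because it is cheap and the study is small (100 to 200 patients planned).

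**What to change.** Add to SAP 6.1.2:

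1. **Every period.** After the existing imputation, require start ≤ own end. Where a known end precedes the imputed start, set the start to that end (start FEB2015 with end 10 Feb becomes one day). Where a period's end and the next start are both partial in the same month, set the end no earlier than its own start and the next start to the day after, keeping both in the recorded month where possible (15 Feb to 15 Feb, next start 16 Feb). Simply imputing each end before the next start is not a remedy: a partial March end would become 31 Mar and the next March start 1 Apr, outside its recorded month.
2. **First on-study period only.** Set the imputed start no earlier than consent. In the example Day 1 becomes 20 Feb and the sample of that day is baseline. This does not apply to the pre-study treatment start of Cohort 2.
3. **Last period.** State that an exact completion-panel last-dose date takes precedence over a month-year end on the dose record when it falls in that month. Otherwise use the earliest of month end, death and cut-off. Do not cap at a last contact date that itself comes from a partial date: 6.1.4 sets such dates to the first of the month, which could place the last dose up to 30 days early.

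The cost is a few lines of SAP text and programming. All dates are already collected, with no protocol amendment and no burden on patients. CSR Appendix 16.1.9 should carry the same wording.

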### 6.1.3 Calculation of "time since prior event" variables

All "time since prior event" variables (e.g. time since diagnosis) will be calculated relative to the date of first dose in the study:

time since prior event (in days) = date of first dose - date of prior event.

If the "time since prior event" variable is reported in months, the result will be divided by 30.4375 (= 365.25/12).

If the date of the prior event is incomplete, the missing parts will be imputed:

- by the first day of the month if only the day is missing
- by the first day of the year (i.e., 01Jan) if day and month are missing.

### 6.1.4 Last contact date

The last contact date is defined as the latest date among the following:

- All assessment dates (e.g. vital signs assessment dates, dates at which questionnaires were completed, imaging dates, dates at which blood samples were taken, ECG dates, etc.)
- Medication dates including study medication and concomitant medications
- AEs start and end dates
- Last known date patient took study drug as reported on the completion panel

If any of the dates for the above measurements are partial dates, the earliest possible date will be used to impute the date (i.e. first day of month if month and year are known, first day of year if only the year is known).

If the last contact date is after the date of death, the last contact date will be set to the date of death.

### 6.1.5 Study day

Study days are calculated relative to the date of first dose during the study. The date of first dose defines Day 1. Day -1 is one day before Day 1, Day -2 two days before Day 1, Day 2 one day after Day 1, and so on. That is, there is no Day 0.

More specifically, the study day is calculated as

study day = (date of assessment/event - date of first dose) + 1

if the assessment or event is on or after the date of first dose, and as

study day = (date of assessment/event - date of first dose)

otherwise.

### 6.1.6 Baseline definition

The last non-missing assessment before or on the day of the patient's first dose during the study is considered the baseline assessment.

If no assessment is available before or on the day of first dose, the missing assessment may be imputed by the earliest post-dose assessment, provided it was performed within a pre-defined time window after first dose and before end of treatment.

Time windows depend on the type of assessment; they are displayed in Table 6-1. Baseline values assessed after first dose will not be used as post-baseline assessments.

**Table 6-1 Time window for baseline assessments (only for cohort 2)**

Type of assessment	Time window after first dose (1)
Vital signs	0 day
ECG	1 week
Pituitary imaging	6 months
Gallbladder imaging	6 months
Quality of Life questionnaires	6 months
Assessment of clinical symptoms of Cushing's disease	1 week
Salivary cortisol	1 week
Blood sample for efficacy parameters (serum cortisol, ACTH, lipids)	1 week
Blood sample for safety tests (hematology, blood chemistry, hormones)	0 days
24-hour urine collection for UFC determination	1 week

(1) Assessments performed during this time window after first dose are accepted as baseline assessment if no assessment was performed before or on the day of the first dose.

### 6.1.7 Time windows

There is no visit schedule and no planned assessment in this non-interventional study. Assessment related data are collected as they become available during the study period. Therefore assessments are assigned to time windows based on the study day on which the assessment is performed. For mean UFC, the sample day of the first urine sample included in the calculation of mean UFC will be used for assignment to time windows.

If there are multiple values within a time window, the assessment closest to the target day of the time window will be used, if not indicated otherwise. If two assessments are equally close (e.g. 7 days before and 7 days after target day), the later will be used.

Time windows will be assigned according to the window schema in Table 6-2 if assessments are expected more frequently than every 6 months. Otherwise the time windows in Table 6-3 will be applied (e.g., for tumor volume, variables related to patient reported outcome questionnaires, findings of gallbladder ultrasound).

**Table 6-2 Time windows**

Window name (1)	Window No.	Target Day	Starting Day of Window	Ending Day of Window
Baseline	1	-	-	1 (2)
Month 1	2	30	2	60
Month 3	3	91	61	136
Month 6	4	183	137	229
Month 9	5	275	230	320
Month 12	6	365	321	458
Month 18	7	550	459	641
Month 24	8	731	642	821
Month 30	9	914	822	1005
Month 36	10	1096	1006	1187
After Month 36	11	-	1188	No upper limit
Last value on treatment		DLD (3)	2	DLD + gap (4)
Day 90 after last dose		DLD + 90 days	DLD+gap+1 days	DLD + 90 days

(1) Windows are named according to their target days. For example, the target day for window Month 6 is  $6 * 30.4375$  days, where 30.4375 is the standard length of a month ( $=365.25/12$ ). The starting day of the window is the midpoint between target day of previous window and current window and the ending day is the midpoint between target day of current window and next window.  
 Note that only post-baseline on-treatment assessments are assigned to windows Month 1, Month 2, etc., up to 'after Month 36'.

(2) For some parameters, the earliest assessment after first dose is used as baseline assessment if no assessment is available before or on the day of first dose. This assessment is then exclusively used as baseline assessment although it falls into a post-baseline window.

(3) DLD = Day of last dose of pasireotide s.c.

(4) gap = number of days after DLD during which assessments and events are considered on-treatment. gap=3 for efficacy analyses, gap=28 for safety analyses

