2.2.1 Endpoints for secondary objectives

- Proportion of patients with a mean UFC \leq ULN at 1, 3, 6, 12, 24 and 36 months after enrolling into the study
- The absolute and percentage change from baseline in biochemical measures of disease activity (mean UFC, serum cortisol, serum cortisol after dexamethasone testing, salivary cortisol, ACTH and fasting serum lipid profile) over time
- Proportion of patients achieving normalization of biochemical measures of disease activity (serum cortisol, serum cortisol after dexamethasone testing, salivary cortisol and ACTH) over time
- The absolute and percentage change from baseline in clinical signs and symptoms (blood pressure, body weight, body mass index, waist circumference) over time
- The proportion of patients with favorable shift from baseline in clinical symptoms of Cushing's disease over time
- The change from the last dose of pasireotide s.c. to 3 months after permanent discontinuation of pasireotide s.c. for patients that discontinue pasireotide s.c. prior to completing the 3-year observation period. This change will be evaluated for all available continuous safety and efficacy parameters
- The absolute and percentage change from baseline in tumor size over time
- The absolute and percentage change from baseline in patient -reported outcome questionnaires (Cushing QoL and EURO QoL) over time
- Incidence of Adverse events and assessments of vital signs, blood pressure, heart rate, body temperature, blood glucose (fasting plasma glucose, HemoglobinA1c), hormones (GH, IGF-I, TSH/free T4), liver enzymes (AST, ALT, alkaline phosphatase, γ GT, total bilirubin), hematology, electrolytes, immunological events (e.g., allergic reactions: rash, pruritus, injection site reactions), gallbladder ultrasound and ECGs assessment values

3 Investigational plan

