3.5 Visit schedule and assessments

This study is observational in nature and does not impose a therapy protocol, diagnostic/therapeutic interventions or a visit schedule. However, in order to help encourage more uniform data collection across study sites and patients a suggested schedule of assessments has been provided in [Table 3-1](#).

Patients will be treated with pasireotide s.c. according to the investigator's judgment and in accordance with the local (country-specific) pasireotide s.c. prescribing information. Available data will be collected at patients' visits to their site.

Table 3-1 Suggested schedule of assessments

Visit/Frequency	Baseline	Monthly	Every 3 months	Every 6 months	Every 12 months	End of Treatment	End Of study
Informed Consent	x						
Demography	x						
Inclusion/Exclusion Criteria	x						
Relevant medical history/Current medical conditions (history of smoking, history of alcohol use, presence of hepatitis B and C infections)	x						
Cushing's disease history	x						
Prior medications - For Cushing's Disease	x						
Coagulation test (Prothrombin time, APTT)	x					x	x
Vital Signs	x	x	x	x	x	x	x
Pregnancy test	x	x	x	x	x	x	x
Clinical symptoms of Cushing's disease	x		x			x	x
Glycemic status, FPG	x ¹	x ²				x ³	x ³
Glycemic status, HbA1c	x ¹		x			x ⁴	x ⁴
Salivary cortisol	x	x ⁵	x			x	x
Serum cortisol after dexamethasone	x	x ⁵	x			x	x
24 hour urine collection - Urinary free cortisol	x	x ⁵	x			x	x
Pituitary imaging local analysis (MRI/CT scan)	x				x	x	x
LFTs (ALT, AST, Alkaline phosphatase)	x ¹	x ⁶	x			x	x
12 lead ECG evaluation - local analysis	x ^{1,7}		x			x	x
Hematology/Blood Chemistry *	x			x		x	x
Thyroid function tests (TSH, Free T4)	x				x	x	x
Gallbladder imaging	x ¹			x	x	x	x
Cushing's syndrome QoL/ Euro QoL-5D health QoL/ Patient Reported outcome (PRO)	x			x		x	x

Visit/Frequency	Baseline	Monthly	Every 3 months	Every 6 months	Every 12 months	End of Treatment	End Of study
Dose Administration Record-Pasireotide s.c	x	At each visit				x	x
Adverse Events	x	At each visit				x	x
Concomitant Medication	x	At each visit				x	x

¹ prior starting treatment with pasireotide s.c
² self-monitoring of blood glucose and/or FPG every week for the 1st two to three months and periodically thereafter, as clinically appropriate.
³ Monitoring of FPG 4 weeks after the end of treatment
⁴ Monitoring of HbA1c 3 months after the end of treatment
⁵ every month for the first 3 month and then every 3 months

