6.5.2 Safety evaluation

For all safety analyses, the safety set will be used. Safety analysis will be stratified by incident or prevalent use of the drug.

Safety and tolerability assessments include AEs, vital signs, blood pressure, heart rate, body temperature, blood glucose (fasting plasma glucose, HemoglobinA1c), hormones (GH, IGF-1, TSH/free T₄), liver enzymes (AST, ALT, alkaline phosphatase, γGT, total bilirubin), hematology, electrolytes, immunological events (e.g., allergic reactions: rash, pruritus, injection site reactions), gallbladder ultrasound and ECGs.

The overall safety observation period will be divided into two mutually exclusive segments:

1. on-treatment period: from day of enrolling into the study to 28 days after last dose of pasireotide s.c.-
2. post-treatment period: starting at day 28+1 after last dose of pasireotide s.c.

Safety data will be largely collected for the on-treatment period.

For continuous safety variables, the change from the last dose of pasireotide s.c. to 3 months after permanent discontinuation of pasireotide s.c. for patients that discontinue pasireotide s.c. prior to completing the 3-year observation period will be summarized.

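### For the safety change after stopping pasireotide, the SAP allows a start value measured up to 28 days off drug, although the protocol defines the change from the last dose

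*SAP*

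**What the plan says.** **Endpoint.** Protocol 2.2.1 lists, for patients who stop before 3 years, "The change from the last dose of pasireotide s.c. to 3 months after permanent discontinuation of pasireotide s.c". Protocol 6.5.2 repeats it for continuous safety variables: "the change from the last dose of pasireotide s.c. to 3 months after permanent discontinuation of pasireotide s.c".

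**Safety periods.** The same protocol section sets the on-treatment period to end 28 days after the last dose. It says that "The overall safety observation period will be divided into two mutually exclusive segments", the second being the "post-treatment period: starting at day 28+1 after last dose of pasireotide s.c".

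**SAP windows.** In Tables 6-2 and 6-3 the row *Last value on treatment* has target day DLD and runs from Day 2 to DLD plus a gap. The row *Day 90 after last dose* runs from the day after that to DLD+90. Footnote 4 sets "gap=3 for efficacy analyses, gap=28 for safety analyses".

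**Choice of value.** SAP 6.1.7 takes the value closest to the target day unless indicated otherwise. On ties: "If two assessments are equally close (e.g. 7 days before and 7 days after target day), the later will be used".

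**Use.** SAP 8.4 compares the on-treatment period with the period from day 28 to day 90 after stopping. It does not say which value represents either period. SAP 8.4.2 to 8.4.4 compare the last on-treatment grade or value with the worst one in the 90 days after discontinuation.

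**Glucose.** Protocol Table 3-1 suggests, in footnote 3, "Monitoring of FPG 4 weeks after the end of treatment" and, in footnote 4, "Monitoring of HbA1c 3 months after the end of treatment".

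**The concern.** A withdrawal comparison needs a start value that reflects the patient on drug. With a gap of 28 days the start value may come from a patient who has been off drug for up to four weeks. Part of any reversal may already have happened, so the measured change after stopping can be too small. The efficacy analyses avoid this with a gap of 3 days.

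Two further points make the result depend on the programmer:

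- The row is named for the last value but has a target day, which matters only under the closest-value rule. The SAP does not say which of the two governs.
- Day 28, the day on which the 4-week fasting plasma glucose (FPG) is suggested, is on-treatment in Table 6-2. In SAP 8.4 it belongs to both periods.

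Hyperglycemia is an important identified risk (Protocol 3.5.2.3), and long-term glycaemic effects are a stated reason for the study (Protocol 1 and 3.2). What patients' glucose does after stopping is therefore one of the more useful things this analysis can show.

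**Working it through.** **1. Reproduce the windows (DLD = 0; Table 6-2).**

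| | Start value no later than | Follow-up window | Length |
|---|---|---|---|
| Efficacy, gap 3 | DLD+3 | DLD+4 to DLD+90 | 90 − 4 + 1 = 87 days |
| Safety, gap 28 | DLD+28 | DLD+29 to DLD+90 | 90 − 29 + 1 = 62 days |

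With a safety start value at DLD+28, the interval measured is between 29 − 28 = 1 day and 90 − 28 = 62 days, against a nominal 90.

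**2. When does an off-drug value become the start value?** Let the last on-drug value be *a* days before DLD and a post-stop value lie at DLD+*d*, with *d* from 1 to 28.

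- 'Last': always.
- 'Closest, ties to the later': only if *a* ≥ *d*.

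Assume on-drug values every *P* days, so that *a* is uniform on 0 to *P* − 1. The spacing is an assumption, since the study imposes no visit schedule.

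| Post-stop value at | *P* = 7 | *P* = 30 |
|---|---|---|
| DLD+7 | 0% | 23/30 = 76.7% |
| DLD+14 | 0% | 16/30 = 53.3% |
| DLD+21 | 0% | 9/30 = 30.0% |
| DLD+28 | 0% | 2/30 = 6.7% |

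Under 'closest' the share is also 0% whenever a value exists on the day of last dose. Under 'last' it is 100% of stoppers who have a value on DLD+1 to DLD+28, by definition.

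**3. Same data, two answers.** Take assumed FPG values of 8.0 at DLD−5, 6.0 at DLD+28 and 5.8 mmol/L at DLD+85.

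- 'Closest' starts from 8.0: 5.8 − 8.0 = −2.2.
- 'Last' starts from 6.0: 5.8 − 6.0 = −0.2.

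**4. Possible attenuation in an affected patient.** Assume exponential reversal with half-life *h* and a follow-up value at DLD+90. A start at DLD+*s* retains (2^(−s/h) − 2^(−90/h)) / (1 − 2^(−90/h)) of the change from the last dose. The half-lives are illustrative and do not come from the documents.

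| *h* (days) | Start at DLD+28 | Start at DLD+3 |
|---|---|---|
| 7 | 6% | 74% |
| 14 | 24% | 86% |
| 28 | 44% | 92% |
| 60 | 57% | 95% |

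**5. The 4-week FPG.** Four weeks is DLD+28, the last on-treatment day in Table 6-2. With assumed uniform scatter around that day, the share falling on or before DLD+28 is:

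- ±3 days: 4/7 = 57.1%
- ±7 days: 8/15 = 53.3%
- ±14 days: 15/29 = 51.7%

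The remaining 42.9%, 46.7% or 48.3% fall in the follow-up window. A shift of one day moves the same measurement from a possible start value to a possible follow-up value.

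**The case against.** **The 28-day boundary belongs to the protocol.** This stands. A reader might infer that the SAP departed from the protocol by using 28 days; it did not. The difficulty is narrower. A period defined for attributing events is also used to pick the start of a change that the same protocol section anchors to the last dose.

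**The SAP has a default rule.** Under 'closest', a day-28 FPG displaces the on-drug value in only 0% to 6.7% of stoppers on the spacing assumed above. The target day in the row supports that reading, which largely answers the worry for FPG if 'closest' governs. But the row name and SAP 8.4.2 to 8.4.4 say 'last', which can be read as the exception that 6.1.7 allows, and SAP 8.4 names no value for the continuous change.

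**The glucose loss is not certain.** Table 3-1 marks FPG at both End of Treatment and End of Study, the schedule is only suggested, and stoppers are followed for 3 months. A later FPG may exist, and HbA1c is suggested at 3 months. A reader might infer that the 4-week FPG is routinely lost from the change analysis; the documents do not show that.

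**Shift-table overlap.** SAP 8.4.2 to 8.4.4 give no start day for the 90 days, so a reader might infer a 28-day overlap with the on-treatment period. The documents do not support it. SAP 8.4, their parent section, defines post-treatment assessments as those made after the on-treatment period, and Table 6-2 starts follow-up at DLD+29. What remains is day 28 itself, which SAP 8.4 puts in both periods.

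**Ending at day 90.** A reader might also object that 90 days is shorter than 3 calendar months. Protocol section 6 itself uses 90 days, so the SAP complies.

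**Conclusion.** The concern holds in limited form. For the safety change after permanent discontinuation, the SAP permits a start value taken up to DLD+28, while the protocol defines the change from the last dose. Under 'last', any value on DLD+1 to DLD+28 becomes the start value. Under 'closest', it does so only if it is at least as near to DLD as the last on-drug value. The direction of the risk is attenuation of whatever reversal follows withdrawal.

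The frequency cannot be derived from the documents. The percentages above rest on assumed visit spacing and scatter, and the retained shares on assumed half-lives. They show that the choice of rule matters, not how many patients are affected.

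The endpoint is secondary and descriptive, no hypothesis is tested, and the primary adverse-event analysis does not use these windows. The point is worth settling before the final analysis, but it does not threaten the study's main conclusion.

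**What to change.** Keep the 28-day on-treatment period for adverse events and routine safety summaries. For the withdrawal comparisons only (the continuous change in SAP 8.4 and the post-discontinuation comparisons in 8.4.2 to 8.4.4):

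1. Take the start value as the last assessment on or before DLD+3, the SAP's own efficacy gap. State in 6.1.7 that 'last' governs this row and that DLD+3 is included. In the example above this gives −2.2.
2. State one follow-up start for the continuous change and the shift tables, so that no value can be on both sides. There are two workable choices:
   - **DLD+28**, which the SAP 8.4 wording already allows, keeps an FPG taken on day 28 as follow-up. An FPG taken on days 25 to 27 would still be unused.
   - **DLD+29** follows Table 6-2 and the protocol's post-treatment segment, but leaves a day-28 FPG unused.
3. Leave the end of the window at DLD+90.

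**Cost.** Low, with no new data: edits to footnote 4 and the affected rows of Tables 6-2 and 6-3, wording in 6.1.7, 8.4 and 8.4.2 to 8.4.4, an entry in SAP section 3, and reprogramming of those outputs.

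**Downsides.** A footnote is needed because values on DLD+4 to DLD+28 are on-treatment in routine safety tables but cannot serve as the start value here. Patients whose only post-baseline value lies in that interval lose their start value, so the number analysed should be shown.
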